## **Study Limitations**

First, the Wrong-Patient RAR measure is designed to identify near-miss errors and does not capture wrong-patient errors that reach patients. However, near-miss errors follow the same causal pathways as errors that reach the patient and cause harm, occur more frequently, and can be reliably measured without the biases inherent in voluntary self-reports by providers. National and international patient safety and regulatory agencies endorse the use of near-miss errors to evaluate safety interventions. Second, orders that are retracted and reordered beyond the 10-minute timeframe (10 minutes to retraction, 10 minutes to reorder) will not be identified by the RAR measure. However, prior work demonstrated that the average retract-and-reorder time was less than 2 minutes; the 10-minute timeframe will detect the majority of retracted near-miss order errors and identify a sufficient number of outcome events to power this study. Finally, this research is limited to only one EHR vendor system. However, when fully rolled out, Epic's clients will provide care for 45%-55% of the U.S. population.

## FINAL STATISTICAL ANALYSIS PLAN

**Descriptive Analysis**. We will use descriptive analysis to examine provider-level, patient-level, order session-level, and order-level covariates for the orders placed in the restricted versus unrestricted mode. Descriptive statistics will be reported as mean and standard deviation for continuous variables, and as count and percentages for categories.

**Orders versus Order Sessions.** If a provider begins placing orders in the wrong patient's record, there is the possibility that several such orders will be placed and then retracted together. Therefore, individual orders do not represent independent opportunities for errors to occur. Orders are clustered within order sessions, defined as a series of orders placed consecutively by a single provider for a single patient that begins with opening that patient's order file and terminates when an order is placed on another patient or after 60 minutes, whichever comes first. Thus the order session, rather than each order, represents an independent opportunity for a wrong-patient error to occur.

**Primary Outcome.** The primary outcome measure, the Wrong-Patient RAR measure, is an electronic query run retrospectively against every order placed during the study period to identify instances in which one or more orders placed for a patient were retracted (cancelled) by the same provider within 10 minutes, and then reordered by the same provider for a different patient within the next 10 minutes (RAR events). The primary outcome is wrong-patient order sessions, defined as order sessions that include a wrong-patient RAR event identified by the Wrong-Patient RAR measure.

**Primary Analysis (Aim 1)**. The primary analysis of the randomized trial is intention-to-treat, with each provider generating a cluster of order sessions. Hence, the order session will be used as the unit of analysis. The primary outcome variable is dichotomous, indicating whether or not each order session contains a wrong-patient RAR event. To determine the effect of trial arm on wrong-patient orders, we will construct a random effects logistic regression model with wrong-patient order sessions as the outcome, and randomization arm as the independent variable, using provider as a random intercept to account for clusters of order sessions within providers. We will estimate the effect of the restricted mode versus the unrestricted mode on the rate of RAR events using the odds ratio and its 95% confidence interval (CI), and will test the null hypothesis using the Wald test with a two-tailed significance level of 0.05. The primary outcome is reported as the number of wrong-patient order sessions per 100,000 order sessions.

**Subgroup Analysis (Aim 2).** Additional analyses of the effect of the restricted mode versus the unrestricted mode in specified clinical locations will be carried out by including indicators for the locations and location-study arm interaction terms in the model. For subgroup analyses, we will compare the rate of RAR events in emergency department, outpatient, and inpatient settings, and more specifically in inpatient units, including medical/surgical, critical care, pediatrics, and obstetrics units. We will construct similar mixed-effects logistic regression models for each predefined subgroup, with a separate model including an interaction term to test the significance of treatment effects across subgroups, using the Wald test for significance.

**As-Treated Analysis**. Because of administrative errors, some providers were not assigned to the trial arm to which they were randomized. Therefore, we will repeat all assessments in as-treated analyses (ie, according to treatment received) such that each order or order session was characterized by the provider's configuration at the time the orders were placed.

For orders placed in the unrestricted mode, we will examine the rate of RAR events and the percentage of orders placed when one, two, three, or four records were open at the time of ordering,

overall and stratified by clinical setting. For these analyses the order will be used as the unit of analysis (rather than the order session), because a provider may open or close patient records while placing a series of orders during a single order session. We will report the number of RAR events per 100,000 orders along with 95% binomial confidence intervals, as well as the percentage of all orders placed under those conditions. These results will be presented for the unrestricted arm overall, and disaggregated by clinical location.

**Sample Size**. For pragmatic reasons, sample size is not determined by the investigators but will represent the data that is available during the study period. Moreover, as noted, orders do not represent independent events, but are clustered within order sessions that, in turn, are clustered within providers. The magnitude of the effects at these levels are not currently known. Based on prior experience in this setting, in 1 year of data collection we expected to obtain approximately 9,000,000 orders in 2,400,000 order sessions, placed by 3,200 distinct providers for 440,000 distinct patients. We assumed 100 wrong-patient order sessions per 100,000 order sessions in the Unrestricted arm, and an intra-provider correlation of 0.01. With accrual of approximately 1,600 providers in each randomization arm, and a trial duration yielding an average of approximately 1,300 order sessions per provider with a coefficient of variation of 1.2, the trial would have >99% power to detect an odds ratio of 0.5 (or lower), 96% power to detect an odds ratio of 0.7.

**Missing Data.** Due to the automatic functioning of the electronic health record, we do not anticipate that there will be missing data concerning RAR events, the system configuration of restricted mode vs. unrestricted mode, the number of records open at the time of placing an order, or provider-level covariates. There may be sporadic missing information regarding the patient-level covariates. In preliminary data, in a data set of more than 11.6 million orders, there were no missing observations for patient age, sex, or race. An indicator for Hispanic ethnicity was missing in just 4 records. With similar levels of missing data, we feel comfortable that restricting regression models to only include cases with complete data will not introduce appreciable levels of bias. If we find that any variables are missing for more than 1 record per 1,000 (after backfilling based on other records involving the same patient), we will extend our analyses to address this. We will presume that data are missing at random and will apply multiple imputation with chained equations.

**Interim Analysis.** To safeguard against the possibility that our intervention actually worsens (increases) the rate of RAR events, and to prevent unnecessary continuation of a study that is already conclusive, we will have a data safety monitoring committee conduct one interim review of the data in the randomized trial. After 6 months, we expect 50% of the data to have been accrued. Using the Lan-Demets alpha spending procedure with symmetric O'Brien-Fleming boundaries, the stopping rule at the interim review will be a z-statistic of magnitude 3.0318 or greater. The associated nominal p-value is 0.0024. Combined with a final analysis using a critical z-value of 1.9669 (nominal P=0.0492), we will have spent our overall alpha of 0.05 at the end of the study. The effects of this interim analysis procedure on nominal statistical power (see above) is negligible, less than 0.5 percentage points, so no adjustments to data collection need be made to account for this.

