Provider-level covariates: type of ordering provider (attending, resident, physician assistant, nurse practitioner, pharmacist, or other), and total number of orders placed during the study period (a measure of the frequency with which the provider uses the system).

Patient-level covariates: age, race, ethnicity, sex, unit, and date and time of admission.

Order-session level covariates: location of the order session (emergency department, medicalsurgical unit, intensive care unit, labor and delivery, pediatrics, other specialty units).

Order level covariates: type of order (medication, imaging, nursing order, procedure, other), date and time of order, date and time of retraction, and number of patient records open at the time the order was placed.

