## Inclusion and Exclusion Criteria

**Patient Inclusion and Exclusion Criteria.** All patients are at risk for wrong-patient orders, so all orders placed for all patients will be included in the study. We will ask to waive informed consent to patient inclusion in this study, as it poses no more than minimal risk to patients. To enhance confidentiality, we will replace medical record numbers with pseudo-identifiers in the analytic data sets prior to analysis.

**Provider Inclusion and Exclusion Criteria.** Any provider who can place an electronic order can potentially place an order on the wrong patient. Prior work showed that wrong-patient errors are made by physicians (60 errors per 100,000 orders), nurse practitioners and physician assistants (74 errors per 100,000 orders), nurses (33 errors per 100,000 orders) and pharmacists (67 errors per 100,000 orders). We will therefore include in the study all providers with the authority to place electronic orders. Providers will be excluded only if their workflow either 1) has a defined requirement to open two patient

records simultaneously (eg, mother-infant services), or 2) bypasses the standard order entry process and therefore would not be captured by the outcome measure (eg, radiologists).

To protect providers' identities, all provider identifiers will be replaced with pseudo-identifiers in the analytic data sets prior to analysis. We will request a waiver of consent from the Institutional Review Board (IRB) as this study poses no more than minimal risk for providers (see Protection of Human Subjects).

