# **Randomization**

All inpatient, emergency department, and outpatient providers will be randomized in a 1:1 ratio to either a maximum of one patient record open at a time (restricted mode), or a maximum of four records open at once (unrestricted mode). Assignments will be made prior to the start of the study, and will remain constant throughout the study. A computer programmer working in the information technology (IT) department, who is not an investigator on this study, will use a computerized random number generator and assign one random number to each provider. Providers assigned odd numbers will be assigned to the restricted arm, and those assigned even numbers will be assigned to the unrestricted arm. Providers will be manually assigned per randomization to EHR user-role templates that differ only in the number of patient records allowed open. Providers newly hired after the start of the study will be assigned a random number when assigned a new user logon for the EHR from a computer programmer not affiliated with the study, and will be added to the appropriate arm based on their assigned random number. The study methodology has been approved by the Senior Vice President and Chief Medical Officer at Montefiore, as well as the Executive Lead for the EHR.

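### Does the primary model lose anything that matters by leaving out provider type?

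*Combined protocol and SAP*

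**What the plan says.** The SAP (Primary Analysis, Aim 1) specifies an intention-to-treat random-effects logistic regression on order sessions, with "randomization arm as the independent variable, using provider as a random intercept to account for clusters of order sessions within providers". No other fixed effect enters. Location appears only in the Aim 2 subgroup models.

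The protocol (Methods, provider-level covariates) lists two items. One is professional role, described as "type of ordering provider (attending, resident, physician assistant, nurse practitioner, pharmacist, or other"). The second is a measure of volume, namely the "total number of orders placed during the study period (a measure of the frequency with which the provider uses the system"). At order-session level it lists "location of the order session (emergency department, medicalsurgical unit, intensive care unit" and further units. The SAP gives these covariates a descriptive role (Descriptive Analysis) and expects no missing provider-level data (Missing Data).

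On differences between types, the protocol (Provider Inclusion and Exclusion Criteria) cites "physicians (60 errors per 100,000 orders), nurse practitioners and physician assistants (74 errors per 100,000 orders), nurses (33 errors per 100,000 orders"). Its figure for pharmacists is 67. On allocation it says "All inpatient, emergency department, and outpatient providers will be randomized in a 1:1 ratio", by odd or even random number and without stratification (Randomization).

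**The concern.** Adjusting for a prognostic baseline factor is normally cheap and can sharpen the treatment estimate. Here the factor is recorded, complete, and appears prognostic: the highest cited rate is 74/33 = 2.2 times the lowest. Randomisation is not stratified, so neither design nor analysis uses it. If type explained much of the variation between providers, the trial would give up power and would be more exposed to chance imbalance between arms. In a logistic model one might also ask whether omitting a prognostic factor shifts the odds ratio being estimated.

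**Working it through.** **Validity.** Type is an attribute of the provider, and the provider is the unit of randomisation. Unmodelled type differences are therefore part of the between-provider variation that the random intercept represents. With simple randomisation there is no stratification factor that the model would have to carry. In the calculation below, a conditional odds ratio of 0.70 becomes 0.7002 in the arm-only model, so the target is the same for practical purposes.

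**Inputs** (SAP, Sample Size and Interim Analysis): 1,600 providers per arm; "an average of approximately 1,300 order sessions per provider with a coefficient of variation of 1.2"; control rate 0.001 per session; intra-provider correlation 0.01; odds ratio 0.7; final critical z 1.9669. Rates by type are the protocol's 60, 74, 33 and 67. *Assumptions:* the provider mix, and that per-order rate ratios carry over to sessions.

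**The plan's own figure.** The SAP states 96% power at an odds ratio of 0.7. This does not come out exactly, and the baseline depends on the method:

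- A comparison of two proportions with design effect 1 + 1,299 × 0.01 = 13.99 gives 80.1%. Weighting for unequal clusters gives 76.1%, and the full design effect 1 + (2.44 × 1,300 − 1) × 0.01 = 32.71 gives 45.0%.
- A log-normal random-intercept model with the correlation on the observed scale gives a standard error of 0.0880 and 98.15%: 0.3567/0.0880 − 1.9669 = 2.09. It is higher because it works with log-scale variance instead of the variance of raw rates.
- A latent-scale correlation gives about 100%.

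The question here is the *change* from adding type, so each reading is checked.

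**Random-intercept model, observed scale.** Total log variance = ln(1 + 0.01 × 0.999/0.001) = ln(10.99) = 2.397. Type explains ln[Σwr²/(Σwr)²], where w is a type's share and r its rate. For the 40/20/35/5 mix, Σwr = 53.70 and Σwr² = 3,140.8, so type explains ln(3,140.8/2,883.7) = 0.085.

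| Physician / NP-PA / nurse / pharmacist (%) | Explained | Residual | SE, arm-only → adjusted | SE fall | Power (%) |
|---|---|---|---|---|---|
| 75/20/0/5 | 0.008 | 2.389 | 0.08792 → 0.08790 | 0.02% | 98.17 → 98.17 |
| 60/20/10/10 | 0.031 | 2.366 | 0.08805 → 0.08773 | 0.4% | 98.14 → 98.21 |
| 50/20/25/5 | 0.064 | 2.333 | 0.08815 → 0.08743 | 0.8% | 98.12 → 98.27 |
| 40/20/35/5 | 0.085 | 2.312 | 0.08817 → 0.08722 | 1.1% | 98.12 → 98.31 |
| 0/50/50/0 (extreme) | 0.137 | 2.260 | 0.08830 → 0.08672 | 1.8% | 98.09 → 98.41 |

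A simpler version, with one log-normal of variance 2.397 for the arm-only model, puts the fall at 0.1% to 0.9% over the first four mixes.

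**Chance imbalance.** For the 40/20/35/5 mix, 0.08817² − 0.08722² = 0.000167, whose square root is 0.013. Chance imbalance in type therefore moves the odds ratio by roughly 1.3%, and the arm-only standard error already includes this.

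**Other readings.**

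- *750 sessions per provider* (2,400,000/3,200): the standard error falls 0.05% to 1.0%; power goes from 95.2–95.3% to at most 95.5%.
- *Provider variance set so that power is 96%* (log variance 2.853): the standard error falls 0.0% to 0.9%; power reaches at most 96.23%, or 96.37% in the extreme mix.
- *Design-effect method:* in the 50/20/25/5 mix type explains 0.0663/9.99 = 0.66% of between-provider variance. The design effect goes from 13.99 to 1 + 12.99 × (1 − 0.0066) = 13.90, and power from 80.1% to 80.3%. With the full design effect it goes from 45.0% to 45.2%.
- *Latent-scale correlation:* total provider variance is 0.01/0.99 × π²/3 = 0.033. Even if type explained all of it, the variance gain would be 8.3%, with power already above 99.99%.
- *Intermediate log variances of 0.25 to 0.5* (not a document figure): variance gains of about 1% to 14%, or 27% in the extreme mix, with power already above 99.9%.

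**The case for a change.** The strongest case for adjusting is that it needs only a sentence or two, and that the true effect may be smaller than planned. The protocol's Preliminary Studies report a 16% odds reduction for one earlier alert. At an odds ratio of 0.84, with the 40/20/35/5 standard errors, power goes from Φ(0.1744/0.08817 − 1.9669) = 50.4% to Φ(0.1744/0.08722 − 1.9669) = 51.3%. That is 0.9 points: real, but not enough to change how the trial would be judged. An assumed threefold rate difference between attendings and residents, for whom the protocol gives only a single physician rate, also yields about 0.9 points under the equal-cluster design effect.

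A second argument is that the Missing Data section discusses regression models with complete covariate data, while no covariate-adjusted model is specified apart from location in the subgroups. That wording is loose, but the primary model is fully defined without it.

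Against adjusting, nearly all the gain comes from nurses, who are not named in the type list. No passage says type is fixed as of randomisation, so a resident who becomes an attending would need a rule. The other provider-level covariate, total orders during the study, and the session location both arise after randomisation and are poor candidates for the primary model. The change would also be late: the SAP is headed final and already reports that "some providers were not assigned to the trial arm to which they were randomized". Replacing one fully specified model at that stage has a cost of its own. What stands is that adjustment would also have been legitimate, as a matter of preference.

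**Conclusion.** The concern does not hold. The arm-only random-intercept model is valid under simple randomisation of providers, omits no design factor and estimates practically the same odds ratio. Adding provider type would lower the standard error by about 1% or less in the observed-scale calculations with non-extreme mixes. On the protocol's cited rates, power would rise by less than one point under every reading of the correlation. Where the precision gain could be larger, power is already close to 100%.

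This rests on assumed provider mixes, on per-order rate ratios carrying over to order sessions, and on the cited rates by type. It does not depend on which baseline power is right. The failure of the stated 96% to reproduce is a separate matter.

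### The Aim 2 location-by-arm test rests on a provider intercept alone; a provider-clustered robust variance would protect it if providers' error odds shift differently between locations

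*Combined protocol and SAP*

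**What the plan says.** The SAP's Primary Analysis (Aim 1) section specifies a logistic model for wrong-patient order sessions with trial arm as the independent variable, "using provider as a random intercept to account for clusters of order sessions within providers". For that analysis the investigators "will test the null hypothesis using the Wald test with a two-tailed significance level of 0.05".

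Subgroup Analysis (Aim 2) extends this by "including indicators for the locations and location-study arm interaction terms in the model". Its main comparison is by setting: "we will compare the rate of RAR events in emergency department, outpatient, and inpatient settings". A comparison across inpatient unit types follows. On the form of the models it says: "We will construct similar mixed-effects logistic regression models for each predefined subgroup". Whether the effect differs between subgroups is then to be examined "with a separate model including an interaction term to test the significance of treatment effects across subgroups, using the Wald test for significance". It names no provider-by-location effect, random slope or robust variance, and it excludes none.

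The covariate list in the protocol's Methods places location among the order-session attributes: "location of the order session (emergency department" and various units. Under Randomization, each provider's arm stays fixed throughout. The SAP's Sample Size section assumes "an intra-provider correlation of 0.01" without saying on which scale, and concedes that the size of the clustering effects is unknown. Neither document says how many providers work in more than one location, or how far a provider's error tendency varies between locations.

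**The concern.** Arm is a provider attribute and location is a session attribute. For providers who work in several locations, the location-by-arm terms compare within-provider location differences across arms. With a single intercept per provider, the model treats those differences as a fixed location shift plus binomial noise. If one provider is relatively more error-prone in the emergency department and another in clinic, sessions in the same provider-location cell are correlated beyond what the model allows. The interaction standard error is then too small.

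The models fitted separately by location do not share the problem, because each has its own provider intercept. The interaction test is the plan's formal evidence on whether the effect varies by setting. If it is too liberal, a setting-dependent effect could be reported when there is none.

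**Working it through.** The SAP states no error rate or power for the interaction test, so it offers no figure on this exact point to reproduce. The nearest is the Aim 1 power of 96% at an odds ratio of 0.7. It is used in step 3 only for what it implies about the ICC scale.

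**1. Inputs.** From Sample Size:
- 2,400,000 sessions / 3,200 providers = 750 per provider. The power statement uses 1,300, so both were run.
- Event rate 0.001, ICC 0.01, coefficient of variation (CV) of cluster size 1.2.

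From the other sections: 1:1 randomization by provider, and three settings, hence a 2-df test. The 0.05 level is stated for the primary test and assumed for the interaction. Also assumed, and varied: the ICC scale, the share of providers who cross locations, and the location-specific share of provider variance.

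**2. Model and ICC scale.** The model as written, for provider i in location k, is logit p = α + βA_i + γ_k + δ_kA_i + u_i, with u_i ~ N(0, σ²). The null is that all δ_k = 0. The data were generated with an added term v_ik ~ N(0, τ²). The location-specific share is τ²/(σ² + τ²), and a provider's between-location correlation is 1 minus that share.
- Proportion scale: Var(p) = 0.01 × 0.001 × 0.999 = 0.00000999. The squared CV of p is 0.00000999/0.001² = 9.99. For lognormal rates the log-odds variance is ln(10.99) = 2.40 (SD 1.55).
- Latent scale: (0.01/0.99) × π²/3 = 0.033 (SD 0.18).

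**3. What the stated power implies.** With 1,600 providers per arm and 1,300 sessions each:
- Design effect 1 + [(1 + 1.2²) × 1,300 − 1] × 0.01 = 32.71 gives 45% power at an odds ratio of 0.7.
- Ignoring the CV, 1 + 1,299 × 0.01 = 13.99 gives 80%.
- Mixed-model weights give 73–77%.
- A latent-scale ICC gives more than 99.9%.

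None of these is 96%. A design effect of about 8.0 would give it. That means a proportion-scale ICC of 7/3,171 = 0.0022 with the CV, or 7/1,299 = 0.0054 without. The log-odds variance is then ln(1 + 0.002208 × 999) = 1.16 or ln(1 + 0.005389 × 999) = 1.85. The stated power therefore fits neither 2.4 nor 0.033; it points to about 1.2–1.9.

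**4. Simulation.** There were 600 trials per scenario, with 3,200 providers, gamma session counts and three locations. The true odds ratio was the same in every location (1.0, or 0.7 in the row marked *). The model as written was fitted by adaptive Gauss-Hermite maximum likelihood. The Monte Carlo standard error near 5% is √(0.05 × 0.95/600) = 0.9 points.

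| Log-odds variance | Sessions per provider | Location-specific share | Providers crossing | Rejection, model-based | Rejection, robust |
|---|---|---|---|---|---|
| 2.4 | 750 | 0% | 100% | 5.8% | 6.0% |
| 2.4 | 750 | 50% | 0% | 4.7% | 4.7% |
| 2.4 | 750 | 25% | 10% | 13.7% | 5.5% |
| 2.4 | 750 | 25% | 30% | 28.3% | 6.7% |
| 2.4 | 750 | 50% | 30% | 35.7% | 6.2% |
| 2.4 | 750 | 25% | 100% | 34.0% | 5.2% |
| 2.4 | 750 | 50% | 100% | 50.0% | 5.8% |
| 2.4 | 1,300 | 50% | 100% | 60.0% | 5.7% |
| 1.0 | 750 | 25% | 30% | 7.2% | 4.7% |
| 1.0* | 1,300 | 25% | 30% | 8.7% | 4.3% |
| 1.0 | 1,300 | 25% | 100% | 14.5% | 5.3% |
| 1.0 | 750 | 50% | 100% | 16.8% | 6.3% |
| 0.5 | 750 | 25% | 30% | 4.8% | 4.5% |
| 0.5 | 750 | 50% | 100% | 8.3% | 4.7% |
| 0.5 | 1,300 | 50% | 100% | 12.2% | 6.2% |
| 0.033 | 750 | 50% | 100% | 6.5% | 7.0% |
| 0.033 | 1,300 | 50% | 100% | 4.7% | 4.2% |

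The first two rows are controls. With no location-specific variance, or with one location per provider, the test holds its level. The excess in the other rows therefore comes from the stated mechanism.

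**5. Check by another method.** A Poisson approximation with lognormal session counts was run 400 times per scenario, at SD 1.55 with every provider crossing. At correlation 0.8, rejection was 36% with sessions spread evenly, 18–24% with 80% in one location, and 8.5% with 95% in one location. At correlation 1 with an even spread it was 6.5%. The primary arm-only test rejected in 5.0% of runs.

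**The case against.** Much of the case on the other side stands.

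- A reader might infer that the test's null hypothesis itself includes uniform provider shifts. It does not. The null is that the location-by-arm coefficients are zero; equal shifts are an assumption behind the variance.
- The SAP is silent on further random terms and robust variances; it does not rule them out. That is true, but an analyst who follows the text would fit the one-intercept model, and that model's standard error can be too small. This goes beyond missing detail.
- Recording location per session does not show that many providers cross settings. The Randomization section speaks of inpatient, emergency department and outpatient providers, which would fit a mostly single-location workforce. This stands, and in that case the inflation disappears.
- A latent-scale ICC is a standard reading for a logistic mixed model, and it removes the problem. The 96% power does not fit that scale, but it does not support a variance of 2.4 either.
- A reader might infer that the error rate at least doubles whenever providers cross locations. The 8.5% result with 95% of sessions in one location, and several rows at variance 1.0 or below, contradict this.
- Specific Aims defines Aim 2 as rates stratified by location, and neither document makes the interaction test a decision rule. That limits the stakes. Any claim that health systems would change record limits because of this test is speculation.

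**Conclusion.** The point holds as a conditional, inexpensive improvement to a secondary analysis. With a provider intercept as the only random term, the interaction Wald test is too liberal if providers cross locations and their log-odds shift differently.

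Across the table's scenarios with crossing and location-specific variance, the size is about 14–60% rejection at log-odds variance 2.4, 7–17% at 1.0 and 5–12% at 0.5. On a latent-scale ICC, or with one location per provider, there is no material inflation. The 14–60% range is not a floor, since it falls lower when crossing providers place nearly all their sessions in one location. Because the deciding quantities are undocumented, the documents do not support saying that the test will in fact reject far too often. They also give no ground for extending the point to the Aim 1 result. Only the three-location test was simulated; the test across inpatient units has the same structure, but its size was not measured.

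**What to change.** Add one sentence to Subgroup Analysis (Aim 2): the Wald tests of location-by-arm terms, for the three settings and for the inpatient units, will use a cluster-robust (sandwich) variance clustered on provider. Carry this into the as-treated repeat, and leave the primary Aim 1 model unchanged. On the same fits, this variance gave 4.2–7.0% rejection in all 17 scenarios above.

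A provider-by-location random intercept is a possible alternative. It was not tested here and may be unstable, because the plan's figures imply only 750 × 0.001 = 0.75 expected events per provider, to be split over locations.

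The cost is one variance option and no new data. Interaction intervals become slightly wider, and some power is lost if providers' location shifts really are uniform.
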